7.2 Assessments Related to Secondary Endpoints

7.2.1 Time to the First Occurrence of a Daily Volume of MoM \geq 500 mL and \geq 750 mL

The volume of MoM produced on each treatment day will be calculated by using recorded weights of expressed milk in the same method as described in Section 7.1.1. The time from randomization to the first treatment day when maternal subjects produce a daily volume of MoM \geq 500 mL and \geq 750 mL will be calculated.

7.2.2 Proportion of Subjects with a Daily Volume of MoM \geq 500 mL and \geq 750 mL

The volume of MoM produced on each treatment day will be calculated by using recorded weights of expressed milk in the same method as described in Section 7.1.1. The proportion of maternal subjects who produce a daily volume of MoM \geq 500 mL and \geq 750 mL will be calculated for every treatment day from Days 1 to 14.

7.2.3 Volume of MoM Produced over Days 15 to 17

Maternal subjects who complete Days 1 to 14 of assigned treatment will be asked to continue recordings of milk expression on milk container labels through the end of Day 17. The volume of MoM produced over Days 15 to 17 will be calculated by using recorded weights of expressed milk in the same way as described in Section 7.1.1.

7.2.4 Volume of MoM Fed to the Infant

The volume of MoM fed to the infant over Days 1 to 14 will be recorded from hospital records. The volume of breastfed milk over Days 1 to 14 will be recorded.

7.2.5 Volume of Formula/Donor Milk Fed to the Infant

The volume of formula or donor milk fed to the infant over Days 1 to 14 will be recorded from hospital records.

7.2.6 Merotocin Concentration in Milk

At Day 3 and Day 10 visits, a milk sample of approximately 2 mL for merotocin concentration analysis will be taken from the milk expressed at the trial center. Samples are taken only if milk production is, at the discretion of the investigator, adequate to meet the needs of the infant.

Analysis of milk concentration of merotocin will be performed by Ferring Bioanalysis Department by means of a validated liquid chromatography tandem mass spectrometry (LC-MS/MS) method using the milk samples obtained at Day 3 and Day 10 visit, if available. The personnel analyzing the milk samples for merotocin will be blinded to treatment allocation when performing the analyses.

7.2.7 Infant Body Weight

Infant body weight will be collected for the day of randomization (or last recorded measurements as available) and for all treatment days from Day 1 to Day 14 where data are available. Infant body weight may not be measured daily, so data can be missing for some treatment days.

7.2.8 Adverse Events (Maternal Subject and Infant)

Frequency and intensity of AEs will be recorded for maternal subjects and for the infant (as available from hospital records). See Section 8.2 regarding collection and recording of AEs. A search for predefined preferred terms (PTs) and reported terms will be conducted on all treatment-emergent AEs (TEAEs) for maternal subjects to identify those that can indicate nasal local tolerability issues.

7.2.9 Safety Laboratory Parameters (Maternal Subjects)

Blood samples for safety laboratory evaluations of clinical chemistry and hematology will be collected at screening and at Day 15/End-of-Treatment visit. The clinical chemistry and hematology analyses will be performed by a central laboratory. Safety laboratory parameters are listed in [Table 6](#).

Table 6 Safety Laboratory Parameters

Clinical Chemistry	Hematology
Alanine aminotransferase	Hematocrit
Albumin	Hemoglobin
Alkaline phosphatase	Mean cellular volume
Aspartate aminotransferase	Mean corpuscular hemoglobin content
Glucose	Mean corpuscular hemoglobin concentration
Calcium	Platelet count
Chloride	Red blood cell count
Cholesterol	White blood cell count with differential count
C-reactive protein	White blood cell morphology
Creatinine	
Gamma-glutamyltransferase	
Phosphate	
Potassium	
Sodium	
Total bilirubin	
Urea (blood urea nitrogen)	

The investigator will review the laboratory results and evaluate and document whether the results are clinically significant or non-significant.

7.3 Assessments Related to Exploratory Endpoints

7.3.1 Plasma Concentration of Merotocin

Blood samples for plasma concentration of merotocin will be collected using an indwelling catheter at pre-dose and at 5, 10, 20, 30, 45, and 60 minutes after dosing at site at Day 3 and Day 10 visits. For the pre-dose sample, sampling should occur a minimum of 3 hours after the previous dose. Blood samples for the analysis of merotocin concentration will be taken in a minimum of 20 maternal subjects.

Analysis of plasma concentration of merotocin will be performed by means of a validated LC-MS/MS method.

7.3.2 Milk Composition

At randomization, Day 3, and Day 10 visits, a milk sample of approximately 4 mL for milk composition analysis will be taken from the milk expressed at the trial center. The milk sample at randomization will be taken prior to randomization. Milk composition including lipids, protein, caloric content, lactose, and Human Milk Oligosaccharides will be assessed by a central laboratory (detailed in the laboratory manual) for each of the 3 milk samples, if available. Samples are taken only if milk production is, at the discretion of the investigator, adequate to meet the needs of the

infant.

7.4 Assessments Related to Post-trial Endpoints

Additional data will be collected from the hospital records of the infant when the infant is discharged from NICU. The additional data (if available) are infant body weight, length and head circumference at time of infant's discharge from NICU, the date when the infant becomes tolerant to full enteral feeding, date of discharge from NICU, number of days the infant requires TPN until discharge from NICU, type of feeding (MoM and formula/donor milk) at time of infant's discharge from NICU, and whether the maternal subject is lactating (i.e., breastfeeding or breast pumping) at time of infant's discharge from NICU.

Concomitant medications and AEs will be collected from hospital records through time of infant's discharge from NICU or until the last milk sample expressed during maternal subject's treatment with IMP is either consumed by the infant or discarded, whichever occurs last. Information on infant's morbidity events of special interest occurring prior to the infant's discharge from NICU, including NEC, intra-ventricular hemorrhage, BPD, RDS, late-onset sepsis, ROP, and hemodynamically significant patent *ductus arteriosus*, are recorded at the time of infant's discharge from NICU based on hospital records. The trial is not powered to draw conclusions on the incidences of these events, but they are collected in order to capture any trends on the impact of feeding patterns on their incidences.

From the follow-up contact about one month after the infant's NICU discharge, the date of any hospital re-admission of the infant occurring since NICU discharge, and the reason for the re-admission will be recorded. Investigators should assess the causal relationship between the reason for such re-admissions and the IMP.

For long-term follow-up, the ASQ-3 will be provided for all infants at 9 months, 18 months and 24 months of corrected gestational age. A primary caregiver of the infant will answer the questionnaire that consists of approximately 30 questions covering five domains of development, including communication, gross motor, fine motor, problem-solving, and personal-social skills. It takes about 15-30 minutes to complete the questionnaire. If a score falls into the black zone of any domain on the scoring summary sheet, standard referral procedures should be followed.

Data from post-trial activities will be provided in an addendum to the clinical trial report.

7.5 Other Assessments

7.5.1 Vital Signs (Maternal Subject)

Vital signs include blood pressure and heart rate. Systolic and diastolic blood pressure and heart rate will be measured for maternal subjects at randomization, Day 3, Day 10 and Day 15/

End-of-Treatment visits. Vital signs will be measured while maternal subject is in sitting position after resting for at least 3 minutes. Vital signs should always be measured before blood sampling.

All recordings will be performed using validated standard equipment. Vital sign assessments may be repeated for quality reasons and the repeat will be used for analysis.

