Note that Day 3, Day 10, Day 15/End-of-Treatment and Day 18/Follow-up visits can all be postponed for a maximum of 2 days.

Trial Activities

Maternal subjects who provide informed consent for participation will enter the screening period as soon as possible following delivery. The screening period runs from the signing of informed consent to randomization and includes an observation period of a minimum of 48 hours for the collection of milk expression data. Maternal subjects should enter the observation period within 144 hours of delivery as soon as the initial eligibility check has been completed and blood sampling for analysis of safety laboratory parameters has been performed. The observation period starts with the first milk expression session using the breast pump (i.e., pumping session) under supervision at the site. The observation period ends with the last pumping session at the trial center prior to randomization. Milk volume produced for the last 24 hours of the observation period (i.e., the 24-hour baseline interval) will be calculated to assess the inadequacy of milk production.

Throughout the trial, maternal subjects will be instructed to express milk; at least 5 times every 24 hours during the observation period and 6 to 8 times every 24 hours during the treatment and post-treatment follow-up periods, including at least once during the night and with no more than 5 hours between milk expression sessions (see milk expression procedures detailed later). Each session of milk expression will be recorded by subjects themselves every day.

Before treatment on the day of randomization, a physical examination of eligible subjects will be performed and vital signs will be recorded. For the analysis of milk composition, if the volume of production is, at the discretion of the investigator, adequate to meet the nutritional needs of the infant, a sample from the milk expressed prior to randomization will be obtained.

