1.3 Benefit/Risk Aspects

The present trial will be the first to provide efficacy data in the target population. As a proof of concept (PoC) trial, the primary purpose is to test the hypothesis that exposure to merotocin results in increased milk production in women with preterm delivery and inadequate milk production.

A double electric breast pump will be provided to all maternal subjects entering the observation period. Maternal subjects will receive lactation counselling comprised of best supportive care for this population at trial entry and ongoing support throughout the trial. This is an important benefit of participation because postnatal lactation support is associated with increased rates of breastfeeding and improved infant outcomes.^{20,21}

A potential benefit of the trial in general is identification of a pharmacologic intervention that will increase the maternal subjects' ability to produce an adequate amount of MoM to meet their infants' nutritional needs. There are known clinical benefits to premature infants receiving human milk, including shorter time to tolerance of full enteral feedings^{3,12,13} and reduced risk of NEC,^{2,3,4,5} ROP,⁶ sepsis,^{7,8} BPD^{9,10,11} and respiratory distress syndrome (RDS)²².

The risk profile to date is described in the Investigator's Brochure.¹⁹ Merotocin has previously been given to healthy women without any significant undesirable effects. During the single ascending dose and multiple ascending dose trial in healthy women, the most frequently reported adverse events (AEs) were headache, dry mouth, and flushing (hot flush). In that trial, an increased heart rate was observed following a constant rate intravenous infusion which gave rise to high plasma concentrations. During the other phase 1 trial that investigated the transfer of merotocin from blood to breast milk in healthy women, the most frequently reported AEs were uterine spasm, breast engorgement, and headache.

Other effects associated with the pharmacological activity that is possibly mediated by the oxytocin receptor may occur. As such, undesirable effects reported for oxytocin following rapid intravenous bolus and intravenous infusions include cardiac arrhythmia, hypotension, bradycardia, and hypersensitivity.

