The present trial is the first investigation in the target population of women with preterm labor and the first investigation with merotocin exposure beyond 45 hours. The proposed dosing regimen is 400 µg intra-nasal dose (divided into two sprays of 200 µg each) administered 6 to 8 times every 24 hours. The nasal spray can be used at consecutive sessions at least two hours apart for a maximum of 8 times every 24 hours. In the multiple ascending dose part of the phase 1 trial, the harmonic mean terminal half-life ($t_{1/2}$) with the 400 µg intra-nasal dose was 0.56 hours. With this $t_{1/2}$, merotocin concentrations are negligible at two hours after dosing (3.6 half-lives) and merotocin is considered to be eliminated at three hours after dosing (5 half-lives).

Regarding exposure of merotocin to the infants, transfer of merotocin from blood to breast milk was not observed in the phase 1 trial in healthy postpartum women specifically investigating this

risk, as the concentration of merotocin in the milk of all subjects was below the lower limit of quantification. Milk samples obtained in the present trial will also be evaluated for merotocin.

The blood sampling performed as part of the trial might be associated with mild discomfort, bruising, and a very rare risk of infection.

In conclusion, the evaluation of the benefits and risks indicates that participation in this trial is associated with a favorable benefit-risk ratio.

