3.6.5 Selection and Timing of Dose for Each Subject

Following intra-nasal administration of merotocin, the time to maximum observed concentration (t_{max}) and $t_{1/2}$ are approximately 12 to 15 minutes and 25 to 35 minutes, respectively.¹⁹ In the phase 1 milk transfer trial, pharmacodynamic effect of merotocin in the form of uterine contractions were observed within 5 to 10 minutes after an intravenous dose equivalent to 400 µg intra-nasally. Therefore, the treatment for the maternal subject is administered intra-nasally as 1 spray in each nostril approximately 5 to 10 minutes before each milk expression session.

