6.1 Trial Flow Chart

Maternal subjects will undergo the procedures at the time points specified in the schedule of events as shown in [Table 3](#). Infants will undergo the procedures at the time points specified in the schedule of events as shown in [Table 4](#).

Table 3 Trial Flow Chart – Mother-related Activities

Procedure	Screening Visit ^a 0-144 hours of delivery	Randomization Visit 96-192 (+4) hours of delivery	Treatment			Follow-up Day 18 ^b /Follow-up Visit
			Day 3 Visit ^b	Day 10 Visit ^b	Day 15 ^b /End-of-Treatment Visit	
Written informed consent	X					
Inclusion/exclusion criteria	X	X ^c				
Demographics	X					
Medical history	X					
Obstetric history ^d	X					
Lactation history ^e	X					
Antenatal and peripartum history ^f	X					
Pre-pregnancy BMI	X					
Instructions and support for providing MoM	X.....					X
Breast pump and data collection instructions	X					
Record weights of milk ^g	X.....	X ^c				X
Dosing (as applicable) and milk expression documentation review	X.....	X ^c				X
Physical examination		X ^c			X	
Vital signs		X ^c	X	X	X	
Blood sampling (safety parameters)	X				X	
Randomization		X				
IMP dispensing and weighing		X	X	X		
IMP administration at trial center		X ^h	X ^h	X ^h		
Milk expression at trial center	X	X ^c , X ⁱ	X	X		
Milk sampling for merotocin concentration ^j			X	X		
Milk sampling for milk composition ^k		X ^c	X	X		
Blood sampling (PK) ^l			X	X		
Drug accountability			X	X	X	
Concomitant medications	X	X	X	X	X	X
Adverse events	X	X	X	X	X	X
End-of-Trial form ^m						X

a Screening period runs from the signing of informed consent to randomization and includes an observation period of a minimum of 48 hours. Maternal subject-related activities may be performed at more than 1 screening visit.

b Day 3, Day 10, Day 15/End-of-Treatment and Day 18/Follow-up visits can be postponed a maximum of 2 days. The maternal subjects should stop the administration of IMP as soon as having completed 14 days' treatment, rather than continue dosing until the Day 15/End-of-Treatment visit.

c Performed before randomization.

d Including parity and pregnancy outcomes.

e Including number and duration of lactation following previous deliveries (if any) and lactation data from the current postpartum period (number of milk expression sessions, timing of the first milk expression attempt, occurrence of skin-to-skin contact, and use of hand expression).

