6.4.2 Day 3 Visit

Day 3 visit can be postponed a maximum of 2 days.

Maternal subject-related activities:

- Weigh the milk collected since the randomization visit and record the corresponding weights for each milk expression session (this can also be performed any day when the maternal subject brings collected milk to the trial center)
- Review dosing and milk expression documentation for completeness and compliance
- Measure vital signs (sitting blood pressure and heart rate)
- If applicable, insert indwelling catheter, collect blood sample for plasma concentration of merotocin (pre-dose sample; a minimum of 3 hours after the previous dose)^b
- Prime and weigh each nasal spray bottle before dispensing the IMP kit
- Have maternal subject administer trial medication prior to milk expression
- If applicable, collect blood sample for plasma concentration of merotocin at 5 minutes after dosing^b
- Have maternal subject express milk at the site and record the milk expression on milk container labels in accordance with instructions provided in the lactation manual for subjects
- Collect a milk sample for analysis of merotocin concentration (Section 7.2.6) and a second milk sample for analysis of milk composition (Section 7.3.2). Samples should be taken from the milk expressed at this visit. Samples are taken only if the amount of available milk exceeds the needs of the infant at the discretion of the investigator
- If applicable, collect blood samples for plasma concentration of merotocin at 10, 20, 30, 45, and 60 minutes after dosing^b
- Record concomitant medications
- Collect and record AEs
- Perform drug accountability, including weighing and collection of used IMP
- Instruct maternal subject to bring all the milk collected (if it has not been brought to the trial center), the milk container labels with recordings of dosing and milk expression, and her nasal spray bottles to the trial center at the Day 10 visit

^b Blood samples for the analysis of merotocin concentration are taken in a minimum of 20 maternal subjects.

Infant-related activities:

Collect the following data from hospital records for all treatment days as available since last visit:

- Record body weight
- Record infant enteral feeds (volume of MoM and formula/donor milk fed to the infant)
- Record concomitant medications
- Collect and record AEs including information on morbidity events of special interest (Section 8.4)

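### No scheduled blood pressure or heart rate reading is timed to follow a dose, so the vital-sign tables are not designed to show short-lived post-dose changes.

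*Combined protocol and SAP*

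**What the plan says.** Section 7.5.1 sets the four occasions: "Systolic and diastolic blood pressure and heart rate will be measured for maternal subjects at randomization, Day 3, Day 10 and Day 15" (End-of-Treatment). It asks for a seated reading after at least 3 minutes of rest and adds that "Vital signs should always be measured before blood sampling".

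The placing of each reading is given elsewhere in the protocol:

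- **Randomization.** The Synopsis and section 3.1.2 state: "Before treatment on the day of randomization, a physical examination of eligible subjects will be performed and vital signs will be recorded". In the flow chart (Table 3) the vital-signs entry for this visit carries the footnote "Performed before randomization".
- **Day 3 and Day 10.** In sections 6.4.2 and 6.4.3 the step "Measure vital signs (sitting blood pressure and heart rate") comes before the pre-dose PK sample and before the on-site dose. No vital-signs step follows the dose.
- **Day 15/End-of-Treatment.** Section 6.4 has women stop dosing once 14 treatment days are complete and not carry on until this visit. After premature discontinuation, section 6.4.4 puts the visit on the day after the last dose.

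On kinetics, section 3.6.5 says that the time to peak and the half-life "are approximately 12 to 15 minutes and 25 to 35 minutes, respectively". Section 1.3 gives a half-life of 0.56 hours for the 400 µg intra-nasal dose, treats the level as negligible at two hours, and says "merotocin is considered to be eliminated at three hours after dosing (5 half-lives").

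On possible effects, section 1.3 reports that in the ascending-dose trial "an increased heart rate was observed following a constant rate intravenous infusion which gave rise to high plasma concentrations". It also lists arrhythmia, hypotension and bradycardia among effects reported for intravenous oxytocin. Section 9.8.3 plans shift tables by treatment group for blood pressure and heart rate, with no breakdown by time since dose.

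**The concern.** A drug that peaks within a quarter of an hour and has a half-life of about half an hour would be expected to produce any direct haemodynamic effect soon after each spray. If every planned reading is placed before a dose or after treatment has ended, an unremarkable shift table says little about that window. A reader of the trial report could still take it as evidence that blood pressure and heart rate are unaffected by dosing.

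The setting makes this worth attention. Characterizing maternal safety is a secondary objective. Section 1.3 calls this the first trial with exposure beyond 45 hours, with up to 8 doses a day for 14 days. Earlier exposure was in healthy women, whereas exclusion criterion 7 here allows preeclampsia. A silent post-dose change would not be measured by anything else in the schedule: the physical examination is at randomization and Day 15 only, and vital signs are not among the Safety Committee inputs listed in section 3.5.

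**Working it through.** **Inputs.** Half-life 0.56 h (section 1.3), with 25 to 35 minutes as the range (section 3.6.5). Time to peak 12 to 15 minutes, that is 0.20 to 0.25 h (section 3.6.5). Pre-dose PK sample at least 3 h after the previous dose, in a minimum of 20 of about 100 women (Table 3 footnotes; sections 3.2 and 7.3.1). IMP administrations at least 2 h apart (section 5.1.1).

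**The protocol's own figures.** Half-lives elapsed = time / half-life.

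- 2 / 0.56 = 3.57, which rounds to the stated 3.6.
- 3 / 0.56 = 5.36, consistent with the stated 5.

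**Fraction of peak remaining.** I assume single-exponential decline from the peak: fraction = 0.5^((t − tmax) / half-life). The first result uses 0.56 h with tmax 0.20 to 0.25 h; the range also covers half-lives of 25 and 35 minutes.

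| Time since dose | Half-life 0.56 h | Range, 25 to 35 min |
|---|---|---|
| 3 h | 0.5^(2.80/0.56) = 3.1% to 0.5^(2.75/0.56) = 3.3% | 1% to 4% |
| 2 h | 0.5^(1.80/0.56) = 10.8% to 0.5^(1.75/0.56) = 11.5% | 5% to 13% |
| 1 h | 0.5^(0.80/0.56) = 37.2% to 0.5^(0.75/0.56) = 39.5% | 26% to 41% |
| 24 h | essentially 0 | essentially 0 |

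Counting from the moment of dosing gives 2.4% at 3 h and 8.4% at 2 h, but those are not fractions of peak.

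**Reading by reading.**

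1. Randomization: before the first dose, so no exposure.
2. Day 3 and Day 10, PK women: the reading precedes the pre-dose sample. With the 3-hour gap already elapsed, at most about 3% of peak remains (1 to 4%).
3. Day 3 and Day 10, other women: the step order puts the reading before the on-site dose, but no minimum gap from the last home dose is given. Exposure depends on when she last dosed, as in the 2 h and 1 h rows.
4. Day 15: off drug by intent.

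Readings timed to follow a dose: 0 of 4.

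**The case against.** The strongest reply is that the gap is narrower than it looks and that other safety routes exist. Several parts of it stand.

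- **The ordering rule.** At Day 3 and Day 10 the sentence in 7.5.1 fixes the order only where blood is drawn, a minimum of 20 women. For the rest the evidence is the order of the visit steps.
- **Off drug.** A reader might infer that every reading is taken without drug on board. The documents do not support that. A non-PK woman who dosed at home an hour earlier could have 37 to 40% of peak. Because treatment days are 24-hour intervals and visits may follow calendar days, a woman randomized at 3 PM is still in treatment Day 14 until 3 PM on calendar Day 15, so a morning visit could precede her last dose.
- **Source of the caution.** The heart-rate finding came from an intravenous infusion with high concentrations, and the other effects from intravenous oxytocin. Sections 1.2 and 3.6.4 report no safety concerns with intra-nasal doses up to 400 µg every 3 hours for 45 hours.
- **Pre-dose readings have value.** With this half-life little accumulation is expected. What is new beyond 45 hours is any sustained effect, which on-treatment pre-dose readings can address.
- **Adverse events.** Section 8.1 counts clinically significant vital-sign findings as adverse events, women are questioned at each visit, and the first dose is taken on site.

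None of this supplies a planned post-dose measurement. Residual exposure in some women is accidental and is not analysed by time since dose, and adverse event reporting will mostly pick up what a woman feels.

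**Conclusion.** The point holds in a limited form. None of the four scheduled readings is timed to follow a dose, and none is placed near the 12 to 15 minute peak. The shift tables are therefore not designed to show short-lived post-dose changes in blood pressure or heart rate.

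Two stronger conclusions are tempting but not supported. One is that the tables cannot show such an effect, or would look the same as under placebo. That would require every reading to be drug-free and the effect to track plasma level. The documents guarantee neither, and they give an onset of uterine effect but no time of offset. The other is that intra-nasal merotocin is known to cause these changes; the documents give only cautions from intravenous use.

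The percentages rest on single-exponential decline from the stated peak. The finding about the schedule does not depend on them. The efficacy analysis is unaffected. This is a low-cost gain in safety information under the trial's own maternal safety objective.

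**What to change.** 1. In section 6.4.2 or 6.4.3, move that visit's vital-sign reading to within the hour after the supervised dose, as near the stated peak as the pumping session allows and after the 3-minute seated rest. Align Table 3.
2. Leave the other visit's reading pre-dose, so that sustained on-treatment effects can still be seen.
3. Record the time since last dose for every reading.
4. In section 9.8.3, present pre-dose and post-dose shifts separately by treatment group, with the randomization reading as baseline.
5. Amend the ordering sentence in 7.5.1 so that in PK women the post-dose reading may follow earlier catheter draws and is taken before the next scheduled draw. As written, it would rule out any reading after the pre-dose sample.

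The cost is protocol wording, one extra recorded time per reading, and a few minutes at a visit where every woman is already dosed on site. There are two downsides. The Day 3 and Day 10 readings would no longer be directly comparable with each other. The post-dose reading would also reflect pumping as well as dosing, since expression starts 5 to 10 minutes after the spray; the placebo group, which follows the same routine, is the control for that.
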